Design and Methodology: This study is a multicenter, open-label study designed to evaluate the HPA axis suppression potential and systemic exposure to clobetasol, when administered as Clobetasol Topical Oil in pediatric subjects, under conditions consistent with anticipated clinical use and under conditions designed to maximize the potential for drug absorption in subjects with moderate to severe AD. The study will consist of three successively younger pediatric cohorts, as safety data allow: 
 • Cohort 1: ≥ 12 to < 18 years; • Cohort 2: ≥ 6 to < 12 years; and • Cohort 3: ≥ 2 to < 6 years. Enrollment into each successively younger pediatric cohort will proceed only after the preceding cohort has been completed and safety and exploratory data (including adverse events [AEs], tolerability assessments, clinical laboratory results, and the percentage of subjects with HPA axis suppression) have been reviewed and agreed to be acceptable for progression to the next cohort. Enrollment into Cohorts 2 and 3 will proceed only if the percentage of subjects with HPA axis suppression in Cohorts 1 and 2, respectively, is $\leq 40\%$.

Name of Sponsor/Company: Hill Dermaceuticals, Inc.
Name of Finished Product: Clobetasol Topical Oil
Name of Active Ingredient: 0.05% clobetasol propionate

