The lack of HPA axis suppression in the study of Clobetasol Topical Oil in adult subjects with psoriasis, in conjunction with the reduced potency of Derma-Smoothe/FS (which is a fluorinated corticosteroid formulated in an oil vehicle substantially similar to that of Clobetasol Topical Oil) along with the efficacy of Derma-Smoothe/FS in moderate to severe AD in children suggests that Clobetasol Topical Oil may have a favorable efficacy and safety profile in the treatment of pediatric subjects with moderate to severe AD. The use of higher potency topical corticosteroids in pediatric patients is supported under some circumstances, such as for disease control during acute episodes, by current US guidelines of care for the management of AD [Eichenfield 2014].

Children are at a greater risk for systemic adverse reactions such as HPA axis suppression than are adults when treated with topical corticosteroids because of a higher ratio of skin surface area to body mass [Eichenfield 2014]. To minimize the risk to pediatric subjects during this clinical trial, the initial pediatric investigation of Clobetasol Topical Oil will begin with children ≥ 12 to < 18 years (Cohort 1), with enrollment of successively younger pediatric age cohorts (Cohort 2: ≥ 6 to < 12 years; and Cohort 3: ≥ 2 to < 6 years) only after safety results (including evaluations of HPA axis function) are available from the previous (immediately older) cohort and are deemed to be acceptable for progression to the next cohort. Enrollment into Cohorts 2 and 3 will proceed only if the percentage of subjects with HPA axis suppression (defined as a cortisol concentration ≤ 18 $\mu\text{g}/100$ mL at approximately 30 minutes after stimulation with cosyntropin) in the previous cohort is $\leq 40\%$.

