9 CONCOMITANT THERAPIES

All concomitant therapies including topical moisturizers, sunscreens, and other skin products must be recorded on the eCRF. All therapies within 30 days prior to Day 1 must also be recorded on the eCRF.

Every effort should be made to keep concomitant therapy and dosing constant during the study. Any changes in concomitant therapies during the study must be recorded on the eCRF at each visit. The reason for any change in concomitant therapies should be reported as, or in conjunction with, an AE except as noted below:

- Prophylactic therapies, such as vaccines, must be recorded on the eCRF but should not be reported as AEs.
- Changes in therapy for pre-existing conditions that are not related to a worsening of the condition must be reported on the eCRF but should not be reported as AEs. The condition must be reported on the eCRF as part of the subject's medical history.

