9.2 Prohibited Medications

The following medications are prohibited during the study:

- Topical corticosteroids, other than the study drug and corticosteroid-containing inhalers (the use of which is permitted as described in Section 9.1), within 3 weeks before Day 1 and throughout the study.
- Topical immunomodulators, such as tacrolimus or pimecrolimus, within 3 weeks before Day 1 and throughout the study.
- Any systemic medications known to affect cortisol levels or HPA axis integrity, within 30 days before Day 1 and throughout the study.
- An acute systemic course of any corticosteroid, or any use of systemic corticosteroid, within 30 days before Day 1 and throughout the study.

- Any biological medication, within 30 days before Day 1 and throughout the study.
- All topical skin products other than study drug except for the subject's normal skin cleansers, moisturizers, emollients, humectants, sunscreens, and makeup (which may be used in accordance with Section 9.1), and the Clobetasol Topical Oil vehicle, which can be used as a moisturizer if desired.
- Bleach baths, phototherapy, tanning beds, and/or excessive sun exposure.
- Any investigational treatments other than study drug.

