10.3 End of Treatment (Day 15)

This visit may occur up to 1 day later than the specified day (i.e., this visit may occur on either Day 15 or Day 16).

The following procedures and evaluations will occur at this visit:

- Collection of predose PK blood sample, to be performed 12±2 hours after the dose of study drug on the previous evening, and within 1 hour before the dose of study drug that will be applied at the study site on this day.
- Collection and review of the completed subject diary from the previous week.
- Collection of study drug from the previous week.
- Study drug application, to be performed by the subject (or the subject's parent, guardian, or caregiver, as applicable) at the site under the supervision of study staff.
- Weighing of study drug (to be completed after the final study drug application that is performed at the site).
- HPA axis suppression test.
- Assessments of AD.
- AE assessments.
- Tolerability assessments.
- Urine pregnancy test (for female subjects of childbearing potential only).
- Review of concomitant medications.
- Collection of postdose PK blood samples, to be performed at 1 (±10 minutes), 3 (±15 minutes), and 6 (±1 hour) hours after study drug application.
- Blood sampling for clinical laboratory evaluations (blood chemistry and hematology).

For subjects who discontinue prematurely from study treatment, the procedures planned for the End of Treatment visit should be performed if possible, with the exception of HPA axis suppression testing if the previous HPA axis suppression test was performed <28 days prior.

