13.5 Masking/Unmasking

Not applicable; this is an open-label study.

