14.4.7 Interim Analyses and Decision to Proceed to the Next Cohort

No interim analyses are planned for this study. However, safety data will be summarized (as necessary) and reviewed after each cohort, to support a decision as to whether to enroll the next, progressively younger age cohort. The decision to progress to the next cohort will be made by the medical monitor in conjunction with the sponsor.

Safety data that will be reviewed for the most recently completed cohort, before the decision is made to proceed with the next younger cohort, include at a minimum:

- Number and percentage of subjects with HPA axis suppression at the End of Treatment visit, in the safety population. The percentage of subjects with HPA axis suppression at the End of Treatment must be $\leq 40\%$; however, the medical monitor together with the sponsor may use judgment as to whether to exclude from this calculation subjects whose HPA axis suppression may have been due to administration of a prohibited medication (such as other topical corticosteroids) known to affect HPA axis function.

- Number and percentage of subjects with TEAEs in the safety population, and tolerability parameters in the safety population. The medical monitor together with the sponsor may decide not to proceed with enrollment into the next, progressively younger cohort if the frequency, severity, seriousness, and/or nature of TEAEs or tolerability findings are unexpected, taking into consideration the known effects of topical corticosteroids and the potency of CP 0.05%.
- Clinically significant treatment-emergent clinical laboratory (hematology and chemistry) findings in the safety population at the End of Treatment visit. The medical monitor together with the sponsor may decide not to proceed with enrollment into the next, progressively younger cohort if the frequency, severity, seriousness, and/or nature of clinical laboratory findings are unexpected, taking into consideration the known effects of topical corticosteroids.

The medical monitor and sponsor representative will document and communicate their joint decision to the investigator before enrollment of the next, progressively younger cohort is allowed to proceed.

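### The 40% limit for opening a younger cohort allows prohibited-medication users to be dropped only if they were suppressed, so the exclusion can lower the percentage but never raise it

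*Protocol*

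**What the plan says.** Protocol 14.4.7 bases the decision on "Number and percentage of subjects with HPA axis suppression at the End of Treatment visit, in the safety population" and requires that percentage to be at most 40%. It then adds that the sponsor and medical monitor "may use judgment as to whether to exclude from this calculation subjects whose HPA axis suppression may have been due to administration"; the drugs meant are prohibited ones known to affect HPA axis function, with other topical corticosteroids as the example. The review takes place after each cohort, and the same two parties decide on progression. On masking, Protocol 13.5 says "Not applicable; this is an open-label study".

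The limit is stated elsewhere without any exclusion. The Synopsis says "Enrollment into Cohorts 2 and 3 will proceed only if the percentage of subjects with HPA axis suppression in Cohorts 1 and 2" is at most 40%, and Protocol 7 and SAP 4.1 repeat this. Protocol 5.2 likewise says "Enrollment into Cohorts 2 and 3 will proceed only if the percentage of subjects with HPA axis suppression (defined as a cortisol concentration" at or below the cut-off) in the previous cohort is at most 40%. Protocol 14.4.1 removes no one from the safety population for protocol deviations.

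The information needed to identify users is already collected. Protocol 9.2 lists the prohibited classes, among them "Any systemic medications known to affect cortisol levels or HPA axis integrity, within 30 days before Day 1 and throughout the study". Protocol 9 says "Any changes in concomitant therapies during the study must be recorded on the eCRF at each visit", and the End of Treatment procedures in 10.3 include "Review of concomitant medications".

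**The concern.** Removing a subject whose result is confounded by another steroid is reasonable in itself. The difficulty is how the subject is chosen. The clause requires the subject to have been suppressed, so selection depends on the outcome being counted. A user who was not suppressed is equally confounded as a test of the study drug but cannot be removed, and helps to keep the percentage down. The only evidential standard is that the medication may have been the cause, and the result is known when the judgment is made.

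This is the only numeric criterion between one cohort and the exposure of younger children. Protocol 5.2 says children are at greater risk of HPA axis suppression than adults and presents the staged cohorts as the means of minimising that risk. A criterion that can be adjusted in one direction only, after the result, gives weaker protection than the unqualified statements in the Synopsis and Sections 5.2 and 7 suggest. These passages do not expressly contradict 14.4.7, but together they do not state one rule.

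**Working it through.** The plan gives no error rate for this criterion, and Protocol 14.2 says the sample size has no statistical basis, so there is no figure of the plan's own to reproduce.

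**Inputs.** From the documents: the 40% limit (14.4.7) and about 24 enrolled to give at least 20 evaluable per cohort (7.1). Hence n = 20 to 24 subjects tested. Assumed, because the documents give no figure: k = 1 to 3 prohibited-medication users per cohort, a true suppression rate p = 50% in non-users and q = 50%, 70% or 90% in users, and every suppressed user dropped.

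**Direction.** Let s of n be suppressed and j suppressed subjects be dropped. Then

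(s − j)/(n − j) − s/n = −j(n − s)/[n(n − j)] ≤ 0.

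The percentage cannot rise. This step needs none of the assumptions.

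**Effect on one decision.** Take n = 24, s = 10 and two users, one suppressed:

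- no exclusion: 10/24 = 41.7%, stop;
- written rule: 9/23 = 39.1%, proceed;
- all users excluded: 9/22 = 40.9%, stop.

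**Highest observed rate that can still pass with up to three dropped.**

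- n = 24: 11/24 = 45.8% becomes 8/21 = 38.1%.
- n = 23: 11/23 = 47.8% becomes 8/20 = 40.0%.
- n = 20: 9/20 = 45.0% becomes 7/18 = 38.9% with two dropped. Dropping one gives 8/19 = 42.1%, which still fails.

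**Probability of passing.** With x suppressed non-users, binomial(n − k, p), and u suppressed users, binomial(k, q), sum the exact probabilities over the outcomes that satisfy:

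- none: (x + u)/n ≤ 0.40;
- written: x/(n − u) ≤ 0.40;
- symmetric (all users out): x/(n − k) ≤ 0.40.

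With p = q = 0.5:

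| n | none | written / symmetric, k = 1 | k = 2 | k = 3 |
|---|---|---|---|---|
| 20 | 0.2517 | 0.2517 / 0.1796 | 0.2821 / 0.2403 | 0.3192 / 0.1662 |
| 21 | 0.1917 | 0.2517 / 0.2517 | 0.2878 / 0.1796 | 0.3238 / 0.2403 |
| 22 | 0.1431 | 0.1917 / 0.1917 | 0.2517 / 0.2517 | 0.3058 / 0.1796 |
| 23 | 0.2024 | 0.2024 / 0.1431 | 0.2267 / 0.1917 | 0.2717 / 0.2517 |
| 24 | 0.1537 | 0.2024 / 0.2024 | 0.2321 / 0.1431 | 0.2617 / 0.1917 |

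Ranges over the 15 combinations of n and k, with p = 0.5:

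| users' rate q | written − none | written − symmetric | symmetric passes more often than none |
|---|---|---|---|
| 50% | 0 to 0.16 | 0 to 0.15 | 8 of 15 |
| 70% | 0 to 0.18 | 0 to 0.10 | 12 of 15 |
| 90% | 0 to 0.18 | 0 to 0.04 | 13 of 15 |

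The largest gap between written and symmetric (n = 20, k = 3, q = 50%) is 0.153. Of this, 0.067 is the written rule being looser than no exclusion, and 0.086 is the symmetric rule being stricter than no exclusion because 40% falls on whole subjects. With q = 50%, written equals symmetric in 4 of 15 combinations and equals no exclusion in 2 of 15 (n = 20 and n = 23, one user). In no outcome does the written rule stop a cohort that either other rule would pass.

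**The case against.** The strongest reply is that nothing turned on this clause. The study stopped in Cohort 1 after 8 subjects (SAP 4.1), the limit was never applied, and the documents plan no restart. That stands, and it confines the point to reuse of the design.

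Second, the size rests on assumed user numbers, one assumed rate in non-users and full use of a discretionary clause. The largest gap against a symmetric rule also arises when the medication has no effect, which fits poorly with a clause about drugs known to affect the HPA axis. That stands too: with users at 90% the gap is at most 0.04. If the rate in non-users is 60%, the maximum gap falls to 0.063, 0.040 and 0.016 for users at 50%, 70% and 90%. The direction does not depend on any of these choices.

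Third, symmetric exclusion is often looser than applying the limit with no exclusion, and increasingly so as the medication's effect grows. This is correct and the sponsor should know it. The argument for symmetry is that selection does not depend on the result, not that it is always stricter.

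Fourth, safeguards exist. Protocol 14.4 already has reviewers see both safety and evaluable summaries, 11.12 requires every deviation to be documented, adverse event, tolerability or laboratory findings can separately prevent progression, and the joint decision is documented. None of these changes who may be dropped from the calculation, and none requires the percentage to be shown with and without the exclusion. The HPA-evaluable population (14.3.2.1) does not select on cortisol, but it too rests on unblinded study-team judgment, so it is not a ready-made substitute.

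**Conclusion.** The concern holds. The direction of the bias follows from the wording and simple algebra. That results are known at the time is an inference, but a secure one: the clause is conditional on suppression and is applied at the review after the cohort. At the planned cohort size, one exclusion can turn a stop into a proceed (10/24 to 9/23). On the stated assumptions, with a 50% true rate in non-users, the clause used in full adds 0 to 0.18 to the chance of passing compared with no exclusion, and 0 to 0.15 compared with excluding all users; the latter gap shrinks as the medication's effect grows. The clause did not affect this study's reported data. It should be corrected before the design is used again.

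**What to change.** Keep the sponsor's 40% limit and state one rule, in the same terms, in the Synopsis, Protocol 5.2, 7 and 14.4.7 and SAP 4.1. If an exclusion is kept:

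1. Name which of the classes in Protocol 9.2 count as HPA-active, and identify their users from the concomitant-medication records before, and blind to, the End of Treatment cortisol results.
2. Exclude every such user from the calculation, suppressed or not.
3. Show the percentage with and without the exclusion, beside the HPA-evaluable figure already required by Protocol 14.4.
4. State in advance which figure is binding. That choice is the sponsor's, and should be made knowing that symmetric exclusion can pass a cohort that the unadjusted percentage would stop.

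The cost is protocol wording, the matching sentence in SAP 4.1 and one extra line in the cohort summary. Medications are already recorded, so only the blinded classification step is new. No extra subjects, visits or samples are needed, and the tables and listings in the current SAP do not change.

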15 ADMINISTRATIVE CONSIDERATIONS

Details of study administration will be provided in a study reference manual.

15.1 Institutional Review Board

The protocol, informed consent documents, any information provided to subjects, recruitment advertisements and any amendments to these items will have IRB approval prior to their use in the study.

Before study initiation, this protocol, the Clobetasol Topical Oil Investigator's Brochure, the informed consent and assent forms, any other written information given to subjects and/or their parent(s), guardian(s), and/or caregiver(s), and any advertisement for subject recruitment must have IRB approval. Documentation of IRB approval must be sent to the sponsor or designee before study drug will be shipped to the site. The investigator should also provide the Clobetasol Topical Oil Investigator's Brochure to the IRB.

The investigator must provide the IRB with reports, updates, and other information (e.g., safety updates, protocol amendments, and administrative letters) according to regulatory requirements and Institution procedures. The IRB must be notified of completion or termination of the study.

Copies of all correspondence with the IRB regarding this study must be sent to the sponsor or its designee. Additionally, the clinical site must maintain an accurate and complete record of all reports, documents, and other submissions made to the IRB concerning this protocol.

15.2 Ethics and Compliance with Good Clinical Practice

The investigator and all study staff will conduct the study in compliance with this protocol and compliance with FDA regulations, all applicable federal, state, and local laws, rules and regulations relating to the conduct of the clinical study, the ethical principles of the Declaration of Helsinki, and the current International Council for Harmonisation (ICH) GCP guidelines.

The rights, safety, and well-being of the study subjects are the most important considerations and prevail over the interests of science and society.

All personnel involved in the conduct of this study must be qualified by education, training and/or experience to perform their assigned responsibilities.

15.3 Informed Consent and Assent

Voluntary assent and informed consent will be given by every subject and/or the subject's legal representative(s), as applicable, prior to the initiation of any study related procedures. The IRB-approved assent and consent forms must include all elements required by FDA, state, and local regulations, and may include appropriate additional elements. Sample assent and informed consent forms containing the required elements of informed consent or assent (as applicable) will be provided by the sponsor or designee. Any changes made to this sample must be approved by

the sponsor or its designee prior to submission to the IRB. After approval by the sponsor or its designee, the assent and informed consent forms must be submitted to and approved by the IRB.

The assent and informed consent forms must be written in a language in which the subject and/or the subject's legal representative(s), as applicable, are fluent. Regulations require that foreign language informed consent and assent forms be submitted to the IRB for approval. The foreign language translation is required to contain a statement of certification of the translation. The investigator must forward a copy of the assent and/or consent form, the certified foreign language translation, and an IRB approval letter to the sponsor.

Prior to the screening evaluation the investigator/designee will explain the study to each potential subject and the subject's legal representative(s). The subject's legal representative(s) must indicate voluntary consent by signing and dating the approved informed consent form. The subject will also indicate voluntary assent by signing and dating the approved assent form, as appropriate and practicable. The consent/assent process will be conducted prior to the start of any study-related procedure. The investigator must retain the original and provide the subject's legal representative with a copy of the consent/assent form(s).

The investigator will maintain documentation that informed consent and assent (as applicable) was obtained prior to the initiation of any study-related procedures.

15.4 Confidentiality of Subject Information

Subject data recorded on eCRFs during the study will be documented in a coded fashion, and all communications and reports regarding this study will identify subjects only by their subject numbers. Complete subject identification will be kept by the investigator for purposes of long-term follow-up, if needed. This information, as well as all medical information resulting from a subject's participation in this study, will be treated with strict adherence to professional standards of confidentiality. Confidentiality of subject records must be maintained to ensure adherence to applicable local privacy regulations.

Data generated for the study should be stored in a limited-access file area and be accessible only to the investigator and authorized personnel, the sponsor and its designee(s), the IRB, and FDA or other relevant regulatory authorities. Medical information resulting from a subject's participation in this study may be given to the subject's personal physician or to the appropriate medical personnel responsible for the subject's welfare, but no information that can be related to a specific individual subject will be released or used in any fashion without the signed written consent of that subject's legal representative.

